2. OBJECTIVES AND PURPOSES

2.1. Context, objectives and justification of the study

Atrial fibrillation (AF) is a heart rhythm disorder caused by abnormal electrical signals from the atria and is characterized by ineffective atrial contraction and irregular heartbeats. AF can occur in three forms: paroxysmal (episodes lasting less than 7 days), persistent or permanent (lasting more than 7 days) and irreversible (1).

Among patients with AF, more than one-third have associated valve disease, characterized by mitral stenosis or valve prosthesis (1). In this case, AF is called "valvular" (2). Conversely, in patients without associated valvular pathology, AF is said to be "non-valvular".

In France, two-thirds of AF patients are 75 years of age and older. The prevalence of AF is about 1% of the general population and increases with age to reach 10% of the population aged 80 years and over. The male/female sex ratio of prevalent cases is 3:2 (3). The absolute number of cases is equivalent between men and women because of the higher life expectancy in women (4).

Several pathophysiological mechanisms, including blood flow stasis, prothrombotic state, and hypercoagulability induced by AF, can lead to stroke (5). Clinical signs may include shortness of breath at rest, fatigue, palpitations, or chest pain. AF accounts for approximately 15% of all strokes (6).

The therapeutic management aims to prevent thromboembolic complications (risk multiplied by 5), in particular the occurrence of ischemic stroke, to reduce symptoms, to prevent recurrence of AF using antiarrhythmic treatment and to improve the quality of life of patients (4). The 2014 Guidelines of the French National Authority for Health recommend initiating an oral anticoagulant (OAC) in AF patients to prevent the risk of stroke in the event of a high thromboembolic risk identified by a CHA2DS2-VASC score greater than or equal to 2. If the score is equal to 1, the initiation is to be discussed according to risk factors. Among the OACs, the antivitamins K (VKA) (warfarin, acenocoumarol - and fluindione until 2017) were considered as the reference drugs until 2017; the direct oral anticoagulant (DOAC) including direct factor Xa inhibitors (rivaroxaban and apixaban) and direct thrombin inhibitor (dabigatran) could be prescribed as an alternative (4). Recommendations concerning the good use of OACs has been updated in 2018 (5). Since then, DOAC can also be prescribed as a first-line treatment in non-valvular AF patients.

The main risk associated with the use of OACs is the occurrence of serious bleeding events requiring careful use and regular treatment reevaluation. Among patients with AF, some populations have this risk of bleeding potentially increased, especially the elderly and frail (8,9), or those having dementia (10). The risk is also increased in patients with coronary arterial disease (CAD) due to antithrombotic therapy with dual antiplatelet and OAC (4). In case of contraindication to oral anticoagulation, in particular because of major risk of bleeding, a left atrial appendage (LAA) occlusion may be considered to prevent the risk of thromboembolism (11,12).

In France, two previous studies published by Santé Publique France described the annual rate of adult patients newly treated with OAC for AF using data from the National Health Data System (SNDS), of which the most recent published in 2021 estimates in 2018 a standardized rate of 410/100,000 inhabitants (6,7). To our knowledge, no such recent French epidemiological data specific to AF unexposed to OAC is available.

The use of OACs and the associated risks were evaluated in the NACORA study conducted in 2014 by the National Health Insurance (CNAM) in collaboration with the National Agency for Medicines and Health Products Safety (ANSM), using data from the SNDS. This study assessed in France, the hemorrhagic and thromboembolic risks in AF patients exposed to VKA and DOAC (rivaroxaban and dabigatran only), over a short exposure periods of 6 months and a study period from 2011 to 2012 (13,14).

Pfizer and BMS laboratories conducted the NAXOS study, following the methodology of the NACORA study, published in 2020, for the reassessment of the reimbursement of apixaban on the data from the SNDS. The NAXOS study compared the 1-year risk of occurrence of stroke and systemic embolism (SE) and major bleeding in patients initiating OACs (apixaban, rivaroxaban, dabigatran, and VKAs) between 2014 and 2016 with AF (15).

By contrast, there is no such data in AF patients unexposed to OAC in France. This study aims to address the lack

of safety data in the population of AF patients unexposed to OAC over a recent period: 2016-2020. It will also serve as an opportunity to update data in the population of exposed patients since no new results have been published since 2016 and to focus on subpopulations most at risk. Furthermore, the study will allow to describe the changes in AF management following the recommendations issued by the HAS in 2018 .

The objectives of the SIFNOS study are:

Primary objective

To estimate the incidence rate of stroke (ischemic or hemorrhagic), major bleeding and death in both non-valvular AF patients exposed to OAC (VKA or DOAC) and unexposed to OAC, overall and in the following subgroups of interest:

- Elderly (≥ 80 years old)
- Patients with CAD
- Frail patients
- Patients reported with active cancer
- Patients reported with previous stroke

Secondary objectives

- To describe the characteristics of non-valvular AF patients exposed and unexposed to OAC
- To compare the incidence rate of stroke, major bleeding, and death between those two populations
- To estimate the annual incidence and prevalence of patients with non-valvular atrial fibrillation (AF), exposed and unexposed to OAC
- To describe the use of oral anticoagulants (OACs) in non-valvular AF patients initiating treatment (AF patients exposed to OAC therapy)
- To compare Healthcare Resource Utilization (HCRU) and associated costs between patients exposed to apixaban, rivaroxaban, dabigatran, VKA and patients unexposed to OACs
- To describe the therapeutic management before/after the first stroke occurring after initiation of OAC exposure

Exploratory objectives

- To identify subgroups among AF patients with similar profile

2.2. Respect of ethics

This study does not involve the collection, use or transmittal of individually identifiable patient / subject data. It will be conducted in accordance with the ethical and French legal framework, the main principles of which: respect for people, beneficence, non-maleficence and justice. It will process only reimbursed pseudonymized data from SNDS.

2.3. Justification of the public interest

Pfizer and BMS need for scientific research purposes, to use the National Health Data System (SNDS) databases in order to have more recent data and to consider any changes in the management of AF patients during the 2016-2020 period and wish to update the NAXOS study (finalized in 2016 and submitted to the authorities in 2020). Unlike the previous NAXOS study, the SIFNOS study will extend the epidemiological data to all patients having non valvular AF (exposed or unexposed to OAC). It will provide data of AF patients, on their socio-demographic characteristics, care pathways and healthcare resource utilization and incidence rate of clinical outcomes. The incidence rate of clinical outcomes, stroke, major bleeding, and mortality will also be studied in AF subpopulations of interest. This knowledge is intended to provide additional data to optimize the management of patients in routine practice.

2.4. Publication and communication of the results

The results of this study could be communicated through a scientific publication in a scientific peer reviewed journal. The publication will be written in collaboration with IQVIA and Pfizer/BMS. Posters or oral presentations will be prepared for relevant scientific events. The results will be presented as supportive evidence in regulatory submissions to French health authorities, if necessary.

3. METHODOLOGY

3.1. Study design

3.1.1. Description of the study design

SINFOS study is an observational retrospective cohort study using French national health insurance claims database (SNDS). A unique extraction of AF patients (exposed or unexposed to OAC therapy) in SNDS data will be used to conduct the study from 2016 to 2020.

The outcomes are assessed by study objective and defined in Appendix 2, Table 1.

3.1.2. Study time periods

Periods and dates of the study

Inclusion period: Patients will be included from January 1st, 2016 to December 31st, 2019 and to December 31st, 2020 in sensitivity analyses.

Note: Given the uncertainty of the impact of the Covid 19 health crisis on the management of AF patients, for all analyses, the 2020 data will be excluded but included in sensitivity analyses.

Index date for the AF population: The index date will correspond to the date of the first diagnosis of AF, identified by the date of the start of LTD or of the index hospital stay (patients newly diagnosed AF during the study period) and if not filled in (i.e. identified by the initiation of an OAC) to the date of initiation of the OAC for OAC new users.

Historical period: A lookback period of 2 years will be considered before the index date in order to distinguish incident and prevalent AF-patients, describe patient's comorbidities, medical history and history of treatments. Consequently, this historical period will start from January 1st, 2014.

Follow-up period Follow-up will start on the index date and end on the date of occurrence of one of the following events: death or the end date of the study (December 31th, 2019 and to December 31st, 2020 in sensitivity analyses, or the date of the last reimbursement of care recorded in the SNDS (patients with no consumption or reimbursement of care in the 12 months following the date of last consumption).

Data extraction period: The data extraction period will start on January 1st, 2014 and end on December 31st, 2020.

3.2. Description and justification of the study population

3.2.1. Study population

This retrospective cohort study focuses on the AF population as described in

[figure not shown]

Figure 1, in Appendix 2.

The inclusion criteria for the AF population are:

- Patients with at least one hospital stay with a principal (PD), related (RD) or associated (AD) diagnosis of code I48 (Atrial fibrillation of the International Classification of Disease 10th version, ICD-10) or with an active Long-Term Disease (LTD) at the index date or during the year with ICD-10 code I48;

OR

- Patients who are new users of OACs for the AF treatment with or without AF diagnosis (PMSI-MSO or LTD), identifying with a validated and published algorithm with a high specificity (c-index 0,93), using a predictive model developed in the NACORA study (14,16). The algorithm for identifying patients exposed to OAC indicated for AF is based on the presence of at least one reimbursement of an OAC (VKA, apixaban, rivaroxaban or dabigatran), without use of the same OAC in the 24 months prior to the first reimbursement date. This algorithm considers reimbursement data for the 6 weeks prior to the first OAC reimbursement to distinguish patients treated for AF from those treated for deep venous thrombosis (DVT) or pulmonary embolism (PE). This algorithm includes data on age, gender, use of treatments as use of beta-blockers, antiarrhythmics, antiplatelets, antihypertensive drug, holter/echocardiography procedures, cardiologist prescriber, D-dimer blood test reimbursement.

The exclusion criteria for the AF population correspond to those applied in the NACORA and NAXOS studies and are:

- Patients with at least one hospital stays with an ICD-10 code in PD, RD or AD for associated valve disease, ICD-10 codes I05 to I09, I34 and I39, or valve surgery;
- Patients treated with an OAC for another indication than AF:
 - o Patients who are new users of OACs for the treatment of pulmonary embolism (PE, ICD-10 code I26), or deep vein thrombosis (DVT, ICD codes I80 to I82);
 - o Patients who are new users of OAC, not indicated for AF, PE and DVT, having in the six weeks preceding the first reimbursement of OAC, an orthopedic procedure (osteoarticular or muscular) of the lower limb (including hip/knee replacement) as corresponding to the indication of primary prevention of venous thromboembolic events (root of the Diagnosis Related Group , DRG D02)

The following table summarizes the criteria for selecting patients from the AF population in the SNDS data.

Cohort	Inclusion criteria	Exclusion criteria
AF Population	
 o Identified patients with AF aged 18 years and older at diagnosis of AF 	
 o - Beneficiaries who are insufficiently identifiable or for whom there are technical

		
constraints in SNDS [fictive pseudoNIR (patient identifier), twins];
 
 ○ - Beneficiaries affiliated to a settlement institution from the oversea French department Mayotte; ○ History of valvular pathology and contraindications to OAC treatment.
--	--	---

Note: Other exclusion criteria will be discussed together with the Scientific Committee

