9.2.1.3 Historical period

The historical period is a period of 2 years before the index date in order to distinguish incident and prevalent AF-patients, describe patient's comorbidities, medical history and history of treatments. Consequently, this historical period starts from January 1st, 2014.

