D-dimer blood test	
Binary variable (Yes / No)
 
Equals to “Yes” if the patient has reimbursements for at least one D-dimer blood test during the 6 weeks preceding the first date of OAC delivery

	
NABM codes: 1021, 1022.
 
Equals to "No" in other cases

Hospitalization for arterial thromboembolic event	
Binary variable (Yes / No)
 
Equals to "Yes" if the patient is hospitalized at least once with any discharge diagnosis (i.e., principal, related or associated diagnosis) of arterial thromboembolic event (ischemic stroke or transient ischemic attack or systemic arterial embolism) during the 6 weeks preceding the first date of OAC delivery
 
ICD-10 codes: I63 (ischemic stroke) except I63.6 (cerebral infarction due to cerebral venous thrombosis, non-pyogenic), G45 (transient ischemic attack), I74, N28, D73.5, K76.3 (systemic arterial embolism).
 
Equals to "No" in other cases

Then, all the variables representing the exclusion criteria will be derived for each AF patients included after the inclusion criteria and the application of the algorithm ([Table IV](#)).

Table IV. Derived variable for the selection of the population – Exclusion criteria

Variable	Definition
Valvular pathology	
Binary variable (Yes/No)
 
Equals to "Yes" if the patient is hospitalized at least once with any discharge diagnosis (i.e., principal, related or associated diagnosis) of valve disease or valve surgery, during historical or inclusion period
 
ICD-10 codes: I05.x, I06.x, I07.x, I08.x, I09.x, I34.x, I39.x
 
CCAM codes (valve surgery): DBAF003, DBAF002, DBAF005, DBAF004, DBAF001, DBPA002, DBPA004, DBPA005, DBPA006, DBPA007, DBMA008, DBMA012, DBMA003, DBMA002, DBMA011, DBKA004, DBKA008, DBKA007, DBKA012, DBKA010, DBKA005, DBKA002, DBKA006, DBKA003, DBKA001, DBKA011, DBKA009, DBMA007, DBMA013, DBMA005, DBMA009, DBMA010, DBMA006, DBMA001, DBMA015, DBMA004, DBLF009, DBLF001, DBLA004, DBBF198, DBSF001, DBEA001.
 
Equals to "No" in other cases

Standard SNDS exclusion criteria	
Binary variable (Yes / No)
 
See Data Management Plan in section Error! Reference source not found.

Moreover, all the variables used to define the sub-populations will be derived for each patient selected in the study population ([Table V](#)).

Table V. Derived variables for the selection of the populations – Sub-populations

Variable	Definition

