Age ≥ 80 years old	
Binary variable (<80 years old / ≥ 80 years old)
 
Derived based on the date of birth attributed to the patient after cleaning the data extraction
 
Equals to:
 
 13. “<80 years old” if the absolute difference between the year of index date and the year of birth is strictly lower than 80 years old 14. “≥ 80 years old” if the absolute difference between the year of index date and the year of birth is upper than 80 years old 
See also Data Management Plan in section Error! Reference source not found.

History of coronary arterial disease (CAD)	
Binary variable (Yes / No)
 
Equals to “Yes” if the patient meets any criterion below on or in the 2 years prior to the index date:
 
 15. Is hospitalized with any diagnosis (i.e., main, related or associated diagnosis) of coronary arterial disease 
ICD-10 codes: I21.x, I22.x, I24.x, I25.x
 
OR
 
 – Is covered by the LTD status for coronary arterial disease at least one day 
ICD-10 codes: I21.x, I22.x, I24.x, I25.x
 
Equals to “No” in other cases

Claims-based Frailty Index (CFI) (for frail patients’ derivation)	
Continuous variable (between 0 and 1)
 
Claims-based frailty index (CFI) estimates a deficit-accumulation frailty index from a clinical assessment using International Classification of Diseases (ICD) diagnosis codes, Current Procedural Terminology (CPT) codes, and Healthcare Common Procedure Coding System (HCPCS) codes in the prior 2 years in administrative claims data.
 
See more details on calculation of CFI in Appendix 22

Frail patients	
Binary variable (Yes / No)
 
Equals to “Yes” if the Claims based Frailty Index (CFI) is upper or equal to 0.20
 
See Table I variable Claims based Frailty Index (CFI)

Active cancer	Binary variable (Yes / No)

Equals to “Yes” if the patient meets any criterion below in the 2 years before index date:
 
16. Is hospitalized with any discharge diagnosis (i.e., main, related or associated diagnosis) of active cancer
 
ICD-10 codes: C00.x to C80.x, D00.x to D09.x, D37.x to D48.x, Z51.0, Z51.1
 
OR
 
 – Is covered by the LTD status for active cancer at least one day 
ICD-10 codes: C00.x to C80.x, D00.x to D09.x, D37.x to D48.x, Z51.0, Z51.1
 
Equals to “No” in other cases
	

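### The valve exclusion can miss prosthetic valves implanted before the data window, because it uses neither a prosthesis-presence code nor long-term disease (LTD) status

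*Protocol*

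**What the plan says.** Both background sections (protocol 2.1, SAP 7.1) describe valvular AF. They state that among AF patients "more than one-third have associated valve disease, characterized by mitral stenosis or valve prosthesis". The selection table in protocol 3.2.1 lists "History of valvular pathology and contraindications to OAC treatment" as an exclusion, with no codes and no time limit.

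The working rule is narrower. The exclusion criteria in protocol 3.2.1 and SAP 9.2.3.2 refer to hospital stays "for associated valve disease, ICD-10 codes I05 to I09, I34 and I39, or valve surgery". SAP Table IV (section 9.4.1) gives the diagnosis list as "I05.x, I06.x, I07.x, I08.x, I09.x, I34.x, I39.x", adds a list of CCAM valve procedures, and requires a hospital record "of valve disease or valve surgery, during historical or inclusion period".

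On timing, protocol 3.1.2 says: "The data extraction period will start on January 1st, 2014 and end on December 31st, 2020". SAP 9.2.1.3 says: "The historical period is a period of 2 years before the index date".

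Other conditions in the SAP are found through hospital stays or LTD. For coronary disease, Table V accepts a patient who "Is covered by the LTD status for coronary arterial disease at least one day". Previous stroke, active cancer and heart failure are handled the same way.

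**The concern.** The plan's definition of valvular AF is a state: the patient carries a prosthesis. The working rule mostly detects an event, the implantation, and only if it falls inside the data window. A patient whose aortic valve was replaced in 2010, and who has had no listed valve diagnosis and no further valve procedure since 2014, meets no exclusion criterion. That patient can enter as incident non-valvular AF.

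At stake are the purity of the cohort for all objectives and, in particular, the comparison in SAP 9.7.4.2. VKA exposure is the reference there for every Cox model, and valve status is not among the covariates in Table XV or in the list in 9.7.4.2. If missed carriers gather in one exposure group, the hazard ratios involving that group shift. If they gather in the VKA group, every reported hazard ratio shifts.

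**Working it through.** **1. Earliest visible implantation.** The first possible index date is 1 January 2016. Subtracting two years gives 1 January 2014, which reproduces the stated start of the historical period and of the extraction. This is the most favourable case. Table IV does not say whether the historical period is the pooled calendar period from 2014 or each patient's own two years. The earliest visible procedure for an index date of 1 January is:

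| Index year | Pooled from 2014 | Own two years, plus inclusion period 2016–2019 |
|---|---|---|
| 2016 | 1 Jan 2014 | 1 Jan 2014 |
| 2017 | 1 Jan 2014 | 1 Jan 2015 |
| 2018 | 1 Jan 2014 | 1 Jan 2016 |
| 2019 | 1 Jan 2014 | 1 Jan 2016 |

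On the second reading, some implantations from 2014 and 2015 are missed as well.

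**2. Code match.** Matching prosthesis codes against the seven listed families (I05, I06, I07, I08, I09, I34, I39) finds none of Z95.2, Z95.3, Z95.4 or T82.0. I35, I36 and I37 do not match either. So a carrier whose later stays mention only non-rheumatic aortic valve disease (I35) is not caught.

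**3. Routes into the cohort.** The SAP's algorithm for new anticoagulant users (9.2.3.1) requires 24 months without any oral anticoagulant, which removes long-term VKA users from that route. The route through an I48 hospital stay or LTD requires only that AF was not diagnosed in the historical period (9.2.3.3.2). One dispensation within 30 days of inclusion then makes the patient exposed (9.2.1.2). A long-term VKA user with a first I48 record in 2016–2019 therefore enters as VKA-exposed. Protocol 2.1 mentions first-line DOAC use since 2018 for non-valvular AF. Together these make VKA a plausible destination for missed carriers, but they do not establish it.

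**4. Illustration of size.** Let f be the carriers' share of VKA person-time and r their event rate relative to other VKA users. If all missed carriers are VKA-exposed, the crude hazard ratio against VKA is multiplied by 1/(1 + f(r − 1)). For example, f = 0.05 and r = 2 gives 1/1.05 = 0.952. Both f and r are assumptions; the documents give neither.

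| f | r = 0.8 | r = 1.5 | r = 2 | r = 3 |
|---|---|---|---|---|
| 1% | 1.002 | 0.995 | 0.990 | 0.980 |
| 5% | 1.010 | 0.976 | 0.952 | 0.909 |
| 10% | 1.020 | 0.952 | 0.909 | 0.833 |

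The effect runs from negligible to material, and its sign reverses when r is below 1.

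**The case against.** The strongest defence is that the list was inherited on purpose. Protocol 3.2.1 says the exclusions are those of NACORA and NAXOS, and the study is meant to update NAXOS. That is a good reason to keep the list available, but not to leave the main cohort at odds with the plan's own definition. A sensitivity analysis on the inherited list preserves comparability.

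Second, the rule is not blind to older prostheses. Any listed diagnosis in any position, or a repeat valve procedure, at any stay in the historical or inclusion period removes the patient. Carriers with AF already recorded in the look-back are prevalent and leave the event comparison. Both points stand. A reader might infer that a prosthesis is detected only if implanted from 2014 on; that goes too far.

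Third, hospital-only definitions occur elsewhere in the SAP (previous TIA, systemic embolism, sleep disorders), and some of its status codes come from a published comorbidity index. So the missing codes do not prove an oversight. They do show that nothing in the data prevents their use: Z95.8 and Z95.9 also define other vascular diseases in Table XIII, and Z94.0 also appears in the contraindication variables.

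A reader might further infer that missed carriers sit almost wholly in the VKA group, have higher event rates, and so make DOACs and unexposed patients look better. The documents do not support that. They state no treatment split or event rate for carriers, and carriers without an anticoagulant could enter as unexposed. Adjustment for age, CHA2DS2-VASc, HAS-BLED, Charlson index, frailty and concomitant drugs could also absorb part of any excess risk.

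**Conclusion.** The gap is real. Followed exactly, the rule admits some prosthesis carriers whom the plan itself would call valvular. This follows from the code list, the hospital-only source and the data start, and needs no outside figure. How many carriers are admitted, and in which exposure groups, cannot be found from the documents. Concentration in the VKA reference group is plausible because the I48 route states no washout, but it remains an inference. The hazard-ratio factors shown, 0.833 to 1.020, are illustrative and should not be read as an estimate of bias. The primary objective is descriptive and the comparison is secondary. The change is worth making because it is cheap and aligns the working rule with the stated definition.

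**What to change.** In protocol 3.2.1 and SAP 9.2.3.2 and Table IV:

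- Add Z95.2, Z95.3 and Z95.4 in any diagnosis position, at least up to and including the index stay. A prosthesis first coded after that stay would still be missed if the window stops there.
- Add LTD cover of at least one day, for the listed valve codes and for these presence codes, as a further exclusion route. An older registration still active in the window would then count.
- State whether the look-back runs from 1 January 2014 for everyone or covers each patient's own two years.
- Report the newly excluded patients by exposure group (VKA, each DOAC, unexposed). This answers the open question of number and placement.
- Keep the NACORA/NAXOS list as a sensitivity analysis.

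The cost is three codes, one LTD check and one extra run of the selection program. The cohort will be slightly smaller and will depart a little from the NAXOS list. LTD will not find everyone: registration is not mandatory (SAP 9.3.1.1) and the data are only partly available for some schemes (SAP 9.9). That is why both routes are needed.
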